### **4.3 Withdrawal of Subjects from Study Treatment and/or Study**

#### **Permanent discontinuation of MEDI4736 and/or tremelimumab**

An individual subject will not receive any further investigational product if any of the following occur in the subject in question:

1. Withdrawal of consent or lost to follow-up
2. Subject is determined to have met one or more of the exclusion criteria for study participation at study entry and continuing investigational therapy might constitute a safety risk
3. Pregnancy or intent to become pregnant
4. Any AE that meets criteria for discontinuation as defined in Section 6.6
5. Adverse event related to tremelimumab, with the exception of toxicities that do not meet the criteria for discontinuation as defined in Section 6.6
6. Grade  $\geq 3$  infusion reaction
7. Subject noncompliance that, in the opinion of the investigator or sponsor, warrants withdrawal; e.g., refusal to adhere to scheduled visits
8. Initiation of alternative anticancer therapy including another investigational agent
9. Confirmation of PD and investigator determination that the subject is no longer benefiting from treatment with MEDI4736

Subjects who are permanently discontinued from further receipt of investigational product, regardless of the reason (withdrawal of consent, due to an AE, other), will be identified as having permanently discontinued treatment.

Clinical Study Protocol

Drug Substance Tremelimumab

Study Number **ESR-14-10744**

Edition Number 8

Date 17 April 2019

Subjects who are permanently discontinued from receiving investigational product will be followed for safety per Section 10.3.1 and Appendix B, including the collection of any protocol-specified blood specimens, unless consent is withdrawn or the subject is lost to follow-up or enrolled in another clinical study. All subjects will be followed for survival. Subjects who decline to return to the site for evaluations will be offered follow-up by phone every 3 months as an alternative.

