**Study Assessments and Criteria for Evaluation:**

**Safety Assessments:**

On the infusion day with MEDI4736 or MEDI4736 + tremelimumab, we will conduct clinical chemistry, hematology, and vitals. Subjects will be followed for 90 days after the last dose for safety to monitor any AEs, SAEs, etc.

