### **5.3.2 Procedures for handling subjects incorrectly enrolled or randomized**

Subjects who are incorrectly enrolled in the study but have not yet received treatment with MEDI4736 or MEDI4736 + tremelimumab will be withdrawn from the study and will receive standard of care treatment for their MPM.

Subjects who are found to have been incorrectly enrolled after receiving treatment will be withdrawn from the study and will receive standard of care treatment for their MPM. Such patients will be replaced by eligible subjects with MPM. These subjects also will be followed for 90 days to track any AEs, SAEs, etc. from the treatment. These subjects will not be included in any data analyses.

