## 7. STUDY PROCEDURES

Subjects with MPM who are eligible for the study will be enrolled. Subjects first will undergo surgical mediastinal lymph node biopsy (cervical mediastinoscopy) and simultaneous surgical biopsy of the pleural tumor by thoracoscopy, at which time tumor tissue (goal of 2 g, which is generally available) and 25 ml of peripheral blood will be collected. These procedures are performed as our standard of care in the treatment of subjects with MPM. Three days to three weeks later subjects will receive either MEDI4736 (15 mg/kg once intravenously) or MEDI4736 (1500 mg once intravenously) + tremelimumab (75 mg once intravenously). Subjects under 30 kg will be treated with weight-based dosing for both MEDI4736 and Tremelimumab combination therapy. These patients are excluded from fixed based dosing to limit endotoxin exposure from the drug preparations. A control group will include patients who are not treated with MEDI4736 or Tremelimumab. One to six weeks after treatment, subjects will undergo resectional surgery including extrapleural pneumonectomy or pleurectomy/decortication at which time the tumor will be removed (typically 200-1000g) and obtained for study. Blood (25ml) also will be obtained for study. In addition, the sixth rib will be extracted at the time of the resectional procedure, as is routinely done during these procedures. After the removal of the tumor, our standard protocol (in the presence of conserved renal function) includes intraoperative heated chemotherapy using a lavage of

Clinical Study Protocol

Drug Substance Tremelimumab

Study Number **ESR-14-10744**

Edition Number 8

Date 17 April 2019

intracavitary cisplatin (Sugarbaker et al, 2013, 2014; Richards et al., 2006). Subjects will be followed for at least 90 days following the administration of the study drug for potential AEs or SAEs related to the study drug. Subjects will be followed for a longer period of time as standard of care.

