### **9.3.1 Study recording period and follow-up for adverse events and serious adverse events**

Adverse events and serious adverse events associated with the investigational product will be recorded from the time of signature of informed consent, throughout the treatment period and including the follow-up period (90 days after the last dose of MEDI4736).

During the course of the study all AEs and SAEs associated with the investigational product will be proactively followed up for each subject. Every effort will be made to obtain a resolution for all events, even if the events continue after discontinuation/study completion.

If a subject discontinues from treatment for reasons other than disease progression, and therefore continues to have tumor assessments, drug-related SAEs must be captured until the patient is considered to have confirmed PD and will have no further tumor assessments.

The investigator is responsible for following all SAEs associated with the investigational product until resolution, until the subject returns to baseline status, or until the condition has stabilized with the expectation that it will remain chronic, even if this extends beyond study participation.

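### Section 4.3 lets safety follow-up of a subject permanently discontinued from study drug stop on entry to any other clinical study, with no 90-day minimum

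*Combined protocol and SAP*

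**What the plan says.** Section 4.3, under permanent discontinuation: "Subjects who are permanently discontinued from receiving investigational product will be followed for safety per Section 10.3.1 and Appendix B", including protocol-specified blood specimens, "unless consent is withdrawn or the subject is lost to follow-up or enrolled in another clinical study". Section 10.3.1 in that sentence is the AE/SAE recording section, printed in the body as 9.3.1. All subjects are then to be followed for survival, and "Subjects who decline to return to the site for evaluations will be offered follow-up by phone every 3 months as an alternative".

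The safety window appears elsewhere without the new-study exception:

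- Synopsis, Safety Assessments: "Subjects will be followed for 90 days after the last dose for safety to monitor any AEs, SAEs, etc".
- Section 7: "Subjects will be followed for at least 90 days following the administration of the study drug for potential AEs or SAEs".
- Section 9.3.1: AEs and SAEs are recorded from consent, "throughout the treatment period and including the follow-up period (90 days after the last dose of MEDI4736"). It adds: "During the course of the study all AEs and SAEs associated with the investigational product will be proactively followed up for each subject".

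Three further passages treat day 90 as the boundary. Section 5.3.2 says of dosed subjects who should not have been enrolled: "These subjects also will be followed for 90 days to track any AEs, SAEs, etc. from the treatment". The paragraph on unresolved adverse events narrows safety follow-up to ongoing drug-related SAEs only after 90 days. The paragraph on post-study events lifts the duty to report new events actively only once the 90-day period is over.

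Section 9.3.3 has its own early end: the SAE reporting period runs to 90 days or to the start of alternative anticancer therapy.

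**The concern.** Withdrawal of consent and loss to follow-up make further safety contact impossible or impermissible. Enrolment in another study does neither, yet 4.3 treats all three alike. Read literally, a registry or supportive-care study would be enough. The sentence also undercuts itself: it invokes the section that sets 90 days and then lets those 90 days be cut.

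The 90 days after the single dose are the plan's own window for drug toxicity. Part of that toxicity is found only by testing: Section 9.1.3.3 notes that hepatitis often shows as raised transaminases without symptoms, and the scheduled bloods stop together with the assessments. The reasons for discontinuation in 4.3 include adverse events and infusion reactions of Grade 3 or more, so the people concerned may be those in whom toxicity is most likely. Under the safety oversight rules, one drug-related SAE can put treatment on hold, so with few treated subjects a single missed event could matter.

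**Working it through.** The plan states no figure that depends on this clause, so there is none to reproduce. The check compares the texts and counts the scheduled items at stake.

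**Step 1. Which text governs?** The three 90-day statements and the three day-90 boundaries make no exception for a new study. Section 4.3 makes one with no minimum time. Nothing in the protocol says which prevails, so the conflict is unresolved.

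**Step 2. What does the exception remove?** Inputs are the Appendix B rows up to month 3: AE/SAE assessment at day 30 and months 2 and 3 (3); hematology at the same times (3); serum chemistry at the same times (3); thyroid function at day 30 (1). Laboratory panels: 3 + 3 + 1 = 7. The examination, vital signs, weight and pregnancy test at day 30 are not counted.

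| Enrolment in another study | AE/SAE assessments lost | Laboratory panels lost |
|---|---|---|
| Before day 30 | 3 | 3 + 3 + 1 = 7 |
| After day 30, before month 2 | 2 | 2 + 2 = 4 |
| After month 2, before month 3 | 1 | 1 + 1 = 2 |

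Month 3 is nominally 3 × 30.44 ≈ day 91. With the Appendix B tolerance of ±1 week it can be done by day 90, so it is counted as the closing assessment of the window.

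**Step 3. How many subjects?** The documents do not say. The upper bound is the 8 + 8 = 16 planned treated subjects. The realistic number is far lower. Section 5.6 gives each subject one dose, so permanent discontinuation mainly fits a stopped infusion, or a dosed subject later classed as discontinued, for example for starting another anticancer agent. Resected subjects have AE/SAE assessment at all visits under the main schedule, and Appendix B is titled for subjects without resection.

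**Step 4. The two phone schedules.** First 12 months, in months:

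- Appendix B: {2, 3, 4, 6, 8, 10, 12} = 7 contacts.
- Section 4.3: {3, 6, 9, 12} = 4 contacts, assuming that the clock starts at the last dose; 4.3 does not say.
- Union: {2, 3, 4, 6, 8, 9, 10, 12} = 8, so adding month 9 to Appendix B satisfies both.

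**The case against.** The best defence is that 4.3 is one loose clause against a rule repeated throughout the protocol. Proactive follow-up of product-associated events for each subject, follow-up of known SAEs to resolution, and reporting of deaths within 90 days all remain. Section 6.2.2 excludes other investigational anticancer therapy during the study, and Section 12.3 ends the study 90 days after the last subject's infusion, so every subject's window lies inside it. This narrows the gap without closing it. Section 4.3 itself lists starting another investigational agent as a reason for discontinuation, and its exception is not limited to anticancer trials.

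A second defence is that Appendix B is titled for subjects who completed drug without resection. That does not remove the point, because 4.3 itself sends discontinued subjects to Appendix B. It does limit it. A reader might infer that every dosed, unresected subject can lose follow-up this way. The documents do not support that: Section 7.1.3 sends completed, unresected subjects to Appendix B directly, without the exception.

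A reader might also infer that adverse events are never asked about by phone. That rests on silence. Section 4.3 leaves the content of the call undefined. The Appendix B phone row is labelled survival status, but the AE/SAE row does not require attendance, and the two rows coincide at months 2 and 3. Likewise, the idea that a subject declining visits has no call inside the window depends on an unstated clock: a first call near day 91 falls inside once a week's tolerance is allowed.

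Finally, Section 9.3.3 also has an early stop without a 90-day floor. That stands as a demand on the remedy: a change to 4.3 alone would leave unclear what happens to AE/SAE recording once SAE reporting has closed.

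**Conclusion.** The point holds as a minor conflict in a safety rule. Section 4.3 allows AE/SAE follow-up and scheduled bloods to end on enrolment in any clinical study at any time, while the rest of the plan commits to 90 days. The most that can be lost per affected subject on the Appendix B schedule, up to month 3, is three assessments and seven panels.

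It would be too strong to say that the protocol has no 90-day safety floor: the floor is missing from the 4.3 exception, not from the protocol. The group affected is probably very small; that judgement rests on the single dose and on how few routes lead to discontinuation, not on any stated count. The primary endpoint and the sample size are unaffected. The phone intervals are a matter of harmonisation, and the lack of specified AE questions by phone is missing detail, not a demonstrated defect.

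**What to change.** In Section 4.3:

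1. State that enrolment in another clinical study does not end AE/SAE assessment or the scheduled Appendix B safety bloods before day 90 after the last dose, with the month 3 assessment counted as the closing one.
2. Record the start date of any new therapy, so that later events can be flagged as possibly confounded.
3. State that the Section 9.3.3 cut-off at alternative anticancer therapy limits only the SAE reporting period, not AE/SAE recording under 9.3.1. Without this sentence, assessments would continue for a subject on new therapy with no stated rule for what is done with the events found.

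As a secondary tidy-up, replace the 3-monthly phone interval in 4.3 with the Appendix B contact times. Saying what the call asks would supply the missing detail.

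The cost is protocol wording, up to three already planned assessments with their bloods kept per affected subject, and some adverse events that cannot be cleanly attributed because another therapy has begun.

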### **Withdrawal of consent**

Patients are free to withdraw their consent to further participation in this trial without prejudice. If consent is withdrawn, the subject will not receive any further investigational product or further study observation.

### **4.4 Replacement of subjects**

We plan to replace subjects who are withdrawn from the study. The subject who replaces the withdrawn subject will receive the treatment (i.e., MEDI4736 only or MEDI4736 + tremelimumab) that was originally intended for the withdrawn subject.

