#### **5.3.1 Procedures for randomization**

After mediastinoscopy + thoracoscopy, eligible subjects with MPM will be randomized in 2:2:1 ratio to one of three arms: MEDI4736 alone, MEDI4736 + tremelimumab, and a control group of neither MEDI4736 nor tremelimumab. A computer-generated randomization scheme may be generated by the Biostatistics Core, Baylor College of Medicine. Randomization will be accomplished via access to a secure website developed by the Biostatistics Core and automatically notified to the study coordinator or the investigator via email. Randomization will be stratified by receiving previous chemotherapy or not.

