## **5.4 Blinding and procedures for unblinding the study**

### **5.4.1 Methods for ensuring blinding**

This is an open-label study design; both investigators and subjects will know which study drug the subject is receiving.

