## **10. STATISTICAL METHODS AND SAMPLE SIZE DETERMINATION**

This is a pilot study designed to show that combination therapy with MEDI4736 and tremelimumab can have a substantial impact on surgically resectable MPM patients. All subjects will be randomized after the mediastinoscopy + thoracoscopy to one of the three arms to receive MEDI4736+tremelimumab, MEDI4736 only, or untreated control. The primary endpoint will be the ratio of intratumoral cytotoxic T cells to regulatory T cells (CD8/Treg) before and after treatment. The secondary endpoints are the percentage of inducible T-cell co-stimulator (ICOS) positive intratumoral CD4 T cells and tumor tissue expression (Ventana assay) of programmed death-ligand 1 (PD-L1) before and after each treatment. Overall and recurrence-free survival will be also measured as the secondary endpoint. These analysis will be post-protocol analysis based upon data obtained from the standard of care follow up in our post-surgical patients. All subjects will undergo surgical resection One to six weeks after the infusion.

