### **10.3 Analysis plan**

There will be two treatment arms (MEDI4736 only and combination MEDI4736+tremelimumab) and one untreated arm (control). Randomization, stratified by receiving previous chemotherapy or not, will help to minimize patient selection biases between three arms. Preliminary tests will be performed to assess whether our data is normally or non-normally distributed. Patient characteristics will be summarized descriptively. Baseline characteristics will be compared by treatment assignment. For our primary objective that compares outcome variable in tissues before and after treatment with combination MEDI4736

Clinical Study Protocol

Drug Substance Tremelimumab

Study Number **ESR-14-10744**

Edition Number 8

Date 17 April 2019

and tremelimumab, we will use a paired t-test in log-transformed ratio of intratumoral cytotoxic T cells to regulatory T cells (CD8/Treg) before and after the treatment. In our secondary objective numerous variable comparisons are made between tumor tissues from untreated patients with from patients undergoing treatment with either MEDI4736 or MEDI4736 + tremelimumab, and between tumor tissues from patients undergoing treatment with MEDI4736 and tumor tissues from patients undergoing treatment with MEDI4736+tremelimumab. In these comparisons, a paired t-test or Student t-tests will be performed. Because approximately 20 comparisons of immune cell populations will be performed, a Bonferroni correction will be applied to correct for multiple comparisons. For the comparison of overall survival and recurrence-free survival between treatment groups, log-rank test will be used. These analysis will be post-protocol analysis based upon data obtained from the standard of care follow up in our post-surgical patients. SAS software will be used for all other statistical analyses.

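### Section 4.4 gives a replacement subject the withdrawn subject's arm, contradicting the rule that all subjects are randomised and exposing the between-arm secondary comparisons to selection

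*Combined protocol and SAP*

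**What the plan says.** Section 4.4 has two sentences. The first is general: "We plan to replace subjects who are withdrawn from the study". The second fixes the arm: "The subject who replaces the withdrawn subject will receive the treatment (i.e., MEDI4736 only or MEDI4736 + tremelimumab) that was originally intended" for the withdrawn person. Its parenthesis lists the two drug treatments and omits control.

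The randomisation text makes no exception for replacements. Section 5.3.1 says that "eligible subjects with MPM will be randomized in 2:2:1 ratio to one of three arms", through a secure website that emails the result to the study coordinator or the investigator, and adds: "Randomization will be stratified by receiving previous chemotherapy or not". Section 10 repeats it: "All subjects will be randomized after the mediastinoscopy + thoracoscopy to one of the three arms". Section 10.3 gives the purpose, which is that stratified randomisation "will help to minimize patient selection biases between three arms".

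Section 5.4.1 states: "This is an open-label study design; both investigators and subjects will know which study drug the subject is receiving". The synopsis gives one centre. Section 4 has the study investigators determine eligibility, and exclusion 21 in Section 4.2 rests on the investigator's opinion. Section 5.3 expects 20 evaluable subjects, 8, 8 and 4 by arm, with evaluable tied to tissue from both thoracoscopy and resection.

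Two other places call for replacement without naming an arm: Section 5.3.2 (subjects wrongly enrolled and already treated) and Section 7.1.2 (subjects found at thoracoscopy not to have mesothelioma).

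**The concern.** A replacement under Section 4.4 is placed, not randomised. The arm is settled when the earlier subject leaves, before the replacement has been identified. If the staff who recruit and judge eligibility know which arm is vacant, they can, without meaning to, accept or pass over a candidate for that slot on fitness, histology or treatment history. The replacement also need not share the withdrawn subject's chemotherapy status, so the stratified balance can be undone as well.

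At stake are secondary objectives 3 to 5. These compare the combination arm with monotherapy, and separately with untreated patients, on CD8/Treg ratio, ICOS-positive CD4 cells and PD-L1. They rely on randomisation to make the arms comparable, and with 8, 8 and 4 subjects a single slot carries noticeable weight.

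**Working it through.** **1. The plan's own figure.** Inputs from the sample-size text in Section 10: baseline mean log ratio 1.94, detectable post-treatment value 2.87, SD 0.808, correlation 0.5, n = 8, alpha 5%, paired t-test. Sidedness is not stated; I take two-sided.

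- Difference: 2.87 − 1.94 = 0.93.
- SD of the paired difference: 0.808 × √(2 × (1 − 0.5)) = 0.808.
- Noncentrality: (0.93 / 0.808) × √8 = 3.26, with 7 degrees of freedom.
- Power from the noncentral t: 79.7%, against the stated 80%. It reproduces.

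No input depends on how a replacement gets an arm, so this figure is unaffected.

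**2. The rules side by side.**

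| Question | Section 4.4 | Sections 5.3.1 and 10 |
|---|---|---|
| How is the arm chosen? | Inherited from the withdrawn subject | Randomised 2:2:1 by website |
| When is it fixed? | Before the replacement is identified | After mediastinoscopy and thoracoscopy |
| Chemotherapy stratum? | Not mentioned | Stratified |
| Which arms? | Two drug arms named | All three |

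A replacement is an eligible subject, so both columns apply to the same person and cannot both be followed.

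**3. Weight of one slot.** In a drug arm of 8, one inherited slot is 1/8 = 12.5% and two are 2/8 = 25%.

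**4. Illustrative bias.** The documents give neither a withdrawal rate nor any measure of how selected patients might differ. Suppose, as my assumption, that k inherited-slot patients in one arm of 8 differ from the rest by s = 0.5 to 1 SD. The bias in that arm's mean is k × s / 8.

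| k | Bias (SD units) | Simulated two-sided type I error, 8 v 8 |
|---|---|---|
| 1 | 0.06 to 0.125 | about 5% |
| 2 | 0.125 to 0.25 | 5.2% to 6.2% |

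The simulation used 100,000 replicates per setting and a nominal 5% t-test. For 8 v 4 with k = 2 the error stayed at about 5%. If the SD of the log ratio is 0.808, the largest bias shown is 0.25 × 0.808 = 0.20 log units, against a planned within-patient change of 0.93.

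**5. The control arm.** If a lost control were in fact not replaced, a two-sided 5% t-test of 8 treated against the remaining controls (difference 0.93, SD 0.808) would have power 39.7% with 4 controls, 33.0% with 3 and 25.0% with 2. These figures show why the rule needs stating; they are not a forecast.

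**The case against.** The strongest reply is that advance knowledge of the slot is an inference. Section 5.4.1 says staff know what a subject is receiving; no text says when a vacancy is disclosed or that the website is bypassed. In an open-label single-centre trial with fixed 8/8/4 targets, late allocations become easier to guess anyway. The comparisons at risk are secondary, in a study that Section 10 calls a pilot, and the illustrated bias is modest. All of that stands and limits the severity. It does not remove the contradiction, and nothing in the documents closes the route: allocations are emailed to the coordinator or investigator, and investigators decide eligibility.

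Four stronger readings are tempting but unsupported.

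- **Controls are never replaced.** The parenthesis in Section 4.4 omits them, but its first sentence covers any withdrawn subject and Section 5.3 still expects 4 evaluable controls. Only the rule for assigning their replacements is missing.
- **The primary test is biased.** It is a paired comparison within the combination arm. Imbalance between arms cannot bias it, although selection can affect which patients that arm represents.
- **Toxicity withdrawals concentrate the inherited slots in the drug arms.** Each drug subject has one infusion. Section 4.3 keeps subjects who stop the product in follow-up, and Section 7.1.3 with Appendix B provides for dosed subjects who are not resected. No text says that such a subject counts as withdrawn under Section 4.4.
- **Every subject without both tissue samples creates an inherited slot.** Missing tissue at thoracoscopy is exclusion 26, and non-mesothelioma is found at the same procedure. Randomisation comes afterwards, so such subjects should ordinarily have no arm to pass on.

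**Conclusion.** The point holds in limited form. Section 4.4 contradicts Sections 5.3.1 and 10. Followed as written, it permits loss of allocation concealment and of stratification for each replaced slot. It also leaves the assignment of a replacement control unspecified.

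Each affected slot is 12.5% of a drug arm, and the exposure is mainly secondary objectives 3 to 5. Bias of 0.06 to 0.25 SD with one or two slots rests on my assumed 0.5 to 1 SD difference. The number of slots cannot be estimated, because no withdrawal rate is given. The primary power calculation is sound. This should be fixed, but it does not undermine the primary analysis.

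**What to change.** Rewrite Section 4.4 along these lines: when a randomised subject is withdrawn and is to be replaced, the vacated allocation, in any of the three arms including control, is returned to the website list within the same chemotherapy stratum and mixed with the unused allocations in concealed random order. Every replacement is assigned through the website, only after eligibility has been confirmed following thoracoscopy. Recruitment continues until 8, 8 and 4 evaluable subjects are reached.

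Then reconcile Section 4.4 with Sections 5.3.1 and 10, and point the replacement sentence in Section 5.3.2 to the same rule. Flag any replacement already assigned directly, and repeat the between-arm comparisons without those subjects as a sensitivity analysis.

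The cost is one paragraph, a small change to the randomisation list and possibly one or two extra randomisations. If a vacated allocation is the only one left in its stratum, mixing conceals nothing; a few surplus entries on the list would help. The 8/8/4 targets should be kept as minimums: with the inputs above, a combination arm ending at 7 would have 71.9% power for the primary test, against 79.7% with 8.
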